5.4. Prior and Concomitant Medications

- Subjects receiving hormonal contraceptives should consider additional methods of contraception as concentrations of ethinyl estradiol may decrease and progesterin level may increase on co-administration with study drug.
- The use of medications for the treatment of HIV, other than study drug, is prohibited.
- Subjects receiving concomitant medications that are highly dependent on CYP3A for clearance and for which elevated plasma concentrations are associated with serious adverse events should consider alternative concomitant medications.
- During the study, subjects may not receive any of the following concomitant medications:
 - Competitors of renal excretion (e.g., probenecid; high-dose non-steroidal anti-inflammatory drugs)
 - Known nephrotoxic drugs (e.g., aminoglycosides, amphotericin B, vancomycin, cidofovir, foscarnet, cisplatin and pentamidine)
- Medications listed in the following table and use of herbal/natural supplements are excluded or should be used with caution while subjects are participating in the study. Any concomitant medication requiring adjustment or discontinuation due to renal impairment or a change in renal function on study should be managed per that drug's prescribing information.

Table 5-1. Prior and Concomitant Medications

Drug Class	Agents Disallowed	Use Discouraged and To Be Used With Caution
Acid Reducing Agents Antacids		Concentration of study drug may decrease with antacids. Subjects may not take antacids (e.g., Tums, Mylanta); the ulcer medication sucralfate (Carafate); or vitamin or mineral supplements that contain calcium, iron or zinc for a minimum of 2 hours before and 2 hours after any dose of study drug.
Alpha Adrenergic Receptor Antagonists	Alfuzosin	
Analgesics		Tramadol, Propoxyphene: Concentrations may increase with study drug(s); clinical monitoring is recommended.
Antiarrhythmics		Amiodarone, Flecainide, Quinidine, Propafenone, Systemic Lidocaine, Mexiletine, Disopyramide: Concentrations may increase with study drug(s) resulting in a potential for cardiac arrhythmias; clinical and ECG monitoring is recommended.
Calcium Channel Blockers	Bepidil	Felodipine, Nifedipine, Nicardipine, Verapamil, Diltiazem, Amlodipine: Concentrations may increase with study drug(s). Clinical and ECG monitoring of subjects is recommended.

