6.8.1. Management of Virologic Failure

- If the viral load is ≥ 50 copies/mL, HIV-1 RNA should be repeated at a scheduled or unscheduled visit 2-4 weeks after the date of the original test with HIV-1 RNA ≥ 50 copies/mL.
- Upon confirmation of HIV-1 RNA ≥ 50 copies/mL, potential causes of virologic failure should be documented. Assessments should include:
 - Adherence
 - Concomitant medication
 - Comorbidities (for example: active substance abuse, depression, other intercurrent illnesses)
- Investigators should discuss the management of all subjects with confirmed virologic failure with the Medical Monitor.
- If virologic failure is confirmed at the scheduled or unscheduled visit and HIV-1 RNA is ≥ 50 copies/mL, the blood samples from the confirmation visit will be used for HIV-1 genotype/phenotype testing.

[figure not shown]
- If genotype/phenotype resistance to study drug is documented, study drugs should be discontinued.
- If no resistance is detected from genotype/phenotype testing, subject may remain on study drug and a repeat HIV-1 RNA should be repeated (2-4 weeks from the date of confirmed test with HIV-1 RNA \geq 50 copies/mL). Investigators should carefully evaluate the benefits and risks of remaining on study drug for each individual subject and document this assessment in the onsite medical record. Investigators who opt to discontinue study drugs for an individual subject must discuss with the Medical Monitor prior to study drug discontinuation.

Please refer to [Figure 6-1](#) for the management of subjects who meet the criteria for virologic failure.

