##### **6.2.2.2. Time to Pure Virologic Failure Analysis**

For subjects who do not experience a confirmed rebound (ie, HIV-1 RNA  $\geq$  50 copies/mL on 2 consecutive visits or the last available HIV-1 RNA  $\geq$  50 copies/mL followed by premature discontinuation of study), subjects will be censored at the last HIV-1 RNA collection date. For subjects who experience confirmed rebound, the time to PVF will be defined as the earlier time of 2 consecutive HIV-1 RNA  $\geq$  50 copies/mL or the last available HIV-1 RNA  $\geq$  50 copies/mL followed by premature discontinuation of study.

Time to PVF will be analyzed using the KM method by Part 1 and Part 2 using the FAS.

Lastly, subjects who failed according to snapshot algorithm, pure virologic failure analysis algorithms, or had premature study drug discontinuation by Week 48 will be listed.

6.2.2.3. Analysis of proportion of subjects with HIV-1 RNA < 50 copies/mL at Weeks 12, 24, and 48 as determined by the US FDA-defined snapshot algorithm

The analysis windows for Weeks 12, 24, and 48 are defined in [Table 3-1](#). All HIV-1 RNA data collected on-treatment (eg, data collected up to 1 day after the last dose date of study drug) will be used in the US FDA-defined snapshot algorithm. Virologic outcome will be defined as the following categories:

- **HIV-1 RNA < 50 copies/mL:** this includes subjects who have the last available on-treatment HIV-1 RNA < 50 copies/mL in the analysis window
- **HIV-1 RNA ≥ 50 copies/mL:** this includes subjects:
  - a. Who have the last available on-treatment HIV-1 RNA ≥ 50 copies/mL in the analysis window, or
  - b. Who do not have on-treatment HIV-1 RNA data in the analysis window and
    - 1) Who discontinue study drug prior to or in the analysis window due to lack of efficacy (note: Lack of efficacy is defined as having the check-box for Lack of efficacy marked on the Study Drug Completion eCRF), or
    - 2) Who discontinue study drug prior to or in the analysis window due to AE or death and have the last available on-treatment HIV-1 RNA ≥ 50 copies/mL
    - 3) Who discontinue study drug prior to or in the analysis window due to reasons other than AE, death, or lack of efficacy and have the last available on-treatment HIV-1 RNA ≥ 50 copies/mL
- **No Virologic Data (in the Window):** this includes subjects who do not have on-treatment HIV-1 RNA data in the analysis window because of the following:

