- c) For glucose grading, as specified in SAP Section 7.2.2.1, the treatment-emergent flag cannot be determined for nonfasting glucose (including glucose results without a known fasting status). As a result, these records will be excluded from the “Maximum Treatment-emergent Toxicity Grade” summary in the “Treatment-emergent Laboratory Abnormalities” or “Treatment-emergent Grade 3 or 4 Laboratory Abnormalities” summary tables. In addition, fasting glucose and nonfasting glucose will be listed as two separate laboratory tests in the “Laboratory Abnormalities” and “Grade 3 or 4 Laboratory Abnormalities” listings. Only a maximum postbaseline toxicity flag will be displayed and the treatment-emergent flag will not be displayed for nonfasting glucose as the treatment-emergent flag cannot be determined for nonfasting glucose.

25) “On-treatment” HIV-1 RNA data in the SAP refer to the data up to 1 day after the date of premature discontinuation of study drug (eg, last dose date).

26) Primary and Efficacy analyses:

- a) Listing for snapshot algorithm outcome:

In addition to flagging the values of HIV-1 RNA  $< 50$  or  $\geq 50$  for snapshot algorithm virologic outcomes, flag the last available HIV-1 RNA value for the following categories:

- i) HIV-1 RNA  $> 50$  copies/mL - Discontinued Study Drug Due to AE or Death and Last Available HIV-1 RNA  $> 50$  copies/mL
- ii) HIV-1 RNA  $> 50$  copies/mL - Discontinued Study Drug Due to Other reason\* and Last Available HIV-1 RNA  $> 50$  copies/mL
- iii) No virologic Data Discontinued Study Drug Due to AE or Death and Last Available HIV-1 RNA  $< 50$  copies/mL

iv) No virologic Data Discontinued Study Drug Due to Other reason\* and Last Available HIV-1 RNA < 50 copies/mL

Note: \* Other reasons include subjects who discontinued study drug due to investigator's discretion, subject decision, lost to follow-up, noncompliance with study drug, protocol violation, pregnancy, and study terminated by sponsor.

- b) For patients discontinued study drugs, if the last HIV-1 RNA (< 50 copies/mL) was on the same day as the start date of a new non-study ARV, the subjects was not a failure for the Snapshot outcome.
- c) For a subject who completed the study drug with Week 48 HIV-1 RNA missing, snapshot outcome for such subject would be "Missing data during the windows but on study drug".

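### SAP Appendix 5 item 26(b) contradicts the snapshot rules in SAP 6.2.2.3 in a narrow case, names no snapshot category, and gives no order of precedence

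*SAP*

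**What the plan says.** **SAP 6.2.2.3** defines the snapshot outcome at Weeks 12, 24 and 48. On the data used: "All HIV-1 RNA data collected on-treatment (eg, data collected up to 1 day after the last dose date of study drug) will be used". There are three categories.

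- The category below 50 copies/mL has a single definition: "this includes subjects who have the last available on-treatment HIV-1 RNA < 50 copies/mL in the analysis window".
- The category at or above 50 copies/mL has two branches: either (a) the last on-treatment value in the window is ≥ 50, or (b) a set of rules for subjects "Who do not have on-treatment HIV-1 RNA data in the analysis window and" who have stopped study drug. Rule b.1) covers those "Who discontinue study drug prior to or in the analysis window due to lack of efficacy", identified by a check-box on the eCRF, with no condition on the last value. Rules b.2) and b.3) cover stops for adverse event or death, and for other reasons, when the last on-treatment value was ≥ 50.
- No virologic data: among others, stops for adverse event, death or other reasons with a last on-treatment value < 50 and none in the window.

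**SAP Appendix 5, item 26(b)** adds a programming rule. Its opening condition reads "For patients discontinued study drugs, if the last HIV-1 RNA (< 50 copies/mL) was". When that sample coincides with the start of a new regimen, the rule gives this outcome: "on the same day as the start date of a new non-study ARV, the subjects was not a failure for the Snapshot outcome". It is not limited by reason for stopping, by analysis window, or to on-treatment values.

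**The concern.** The two texts can classify the same subject differently, and the subject concerned is one taken off study drug for lack of efficacy. The protocol makes the sequence possible. Protocol 6.6 lists virologic failure among the reasons to stop, and Protocol 6.8.1 states "If genotype/phenotype resistance to study drug is documented, study drugs should be discontinued". The notes to Protocol Figure 6-1 provide for a new regimen with the subject remaining in the study. Protocol 6.4.1 allows the early discontinuation visit up to 72 hours after stopping, whereas on-treatment data end 1 day after the last dose. A sample from that visit, drawn on the day the new regimen starts, may therefore be on-treatment or off-treatment.

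At stake is the snapshot count of subjects with HIV-1 RNA ≥ 50 copies/mL. The SAP definition of pure virologic response (6.1.1.1) does not require a subject to stay on study drug, so the snapshot is where a stop for lack of efficacy is itself turned into a response category. In the conflict cases, applying 26(b) can only lower the ≥ 50 count.

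**Working it through.** **Step 1. Apply 6.2.2.3 to each case that 26(b) describes.** In every row the last HIV-1 RNA is < 50 and was drawn on the start date of a new ARV. The off-treatment rows assume no on-treatment value in the window, which is the condition for branch b.

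| Switch-day sample | Reason for stopping | Result under 6.2.2.3 | Against 26(b) |
|---|---|---|---|
| On-treatment, in window | Any, including lack of efficacy | < 50 | Agrees |
| On-treatment, before window | Lack of efficacy | ≥ 50, by b.1) | Conflict |
| On-treatment, before window | AE, death or other | No virologic data | Category unclear |
| More than 1 day after last dose | Lack of efficacy | ≥ 50, by b.1) | Conflict |
| More than 1 day after last dose | AE, death or other; last on-treatment value ≥ 50 | ≥ 50, by b.2) or b.3) | Conflict |
| More than 1 day after last dose | AE, death or other; last on-treatment value < 50 | No virologic data | Category unclear |

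The condition of no on-treatment value in the window is easy to meet at later time points. The Week 48 window in SAP Table 3-1 opens on Day 295, so anyone whose last on-treatment sample predates Day 295 meets it for Week 48.

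Item 26(b) does not say whether *last* means the last on-treatment value or the last value of any kind. If it means on-treatment, only the b.1) conflict remains. If it means any value, the b.2) and b.3) conflicts arise too, but only for subjects with no later HIV-1 RNA.

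**Step 2. Look for a category and an order of precedence.** Not being a failure could mean < 50 copies/mL or no virologic data. Item 26(b) does not choose. Neither it nor 6.2.2.3 says which text prevails.

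**Step 3. Size one reclassified subject.** The plan gives no figure on this point. The one input is n = 64, the reduced sample size in SAP 1.3; SAP 6.2.2.3 calls for exact 95% intervals.

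- One subject: 1/64 = 1.56 percentage points.
- ≥ 50 category, 0/64: upper limit = 1 − 0.025^(1/64) = 5.6%. Interval 0 to 5.6%.
- ≥ 50 category, 1/64: the upper limit p solves (1 − p)^64 + 64p(1 − p)^63 = 0.025, giving p = 8.4%. Interval 0.04% to 8.4%.

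The Full Analysis Set may be smaller than 64, because SAP 3.1.2 excludes some subjects by baseline regimen. With an assumed 60, one subject is 1/60 = 1.67 points, and the upper limits are 6.0% for 0/60 and 8.9% for 1/60.

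**The case against.** The best defence is that 26(b) is only a programming clarification. It follows item 25, which defines on-treatment data, and item 26(a), whose discontinuation categories are adverse event, death and other reasons, with lack of efficacy not among them. On that reading it says merely that a value < 50 drawn on the day of the switch is not discarded. This may well be the intent, but the sentence applies to discontinued subjects generally and states no such limits.

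The defence is right that the case is rare. A conflict with b.1) needs the lack-of-efficacy box ticked, no on-treatment value in the window, a last value < 50, and that sample drawn exactly on the new-ARV start date. The event is also visible elsewhere. A subject with confirmed rebound is a pure virologic failure whatever a later value shows (SAP 6.1.1.1, and similarly at Weeks 24 and 48). SAP 6.1.1.2 cross-classifies failure with discontinuation, and 6.2.2.2 lists subjects who failed or stopped study drug by Week 48. SAP 6.2.1 labels the snapshot a sensitivity analysis.

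A reader might also infer that the plan credits study drug with suppression achieved by another ARV added during treatment, because 6.2.2.3 contains no rule on new ARVs. The documents do not support taking that further. Item 26(b) concerns subjects who have discontinued. Protocol 5.4 states "The use of medications for the treatment of HIV, other than study drug, is prohibited", and SAP 7.5.1 lists all non-study ARVs. The SAP also has an Appendix 2 flowchart of the algorithm, whose content is not in the text available to me, so a rule there cannot be excluded. An automatic ≥ 50 classification for such subjects would be a new rule without support in either document.

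**Conclusion.** The contradiction is real but narrow. A subject stopped for lack of efficacy, with no on-treatment HIV-1 RNA in the window and a last value < 50 on the new-ARV start date, is ≥ 50 copies/mL under 6.2.2.3 b.1) and not a failure under 26(b). Taken literally, 26(b) can also clash with b.2) and b.3) through off-treatment samples.

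Three stronger readings are not supported.

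- That 26(b) *overrides* 6.2.2.3: no precedence is stated in either direction, and where an on-treatment value < 50 lies in the window the two texts agree.
- That the < 50 rate rises, for example from 63/64 to 64/64: this assumes that not being a failure means < 50. If it means no virologic data, the < 50 count does not change.
- That the primary endpoint is at risk: the Week 12 pure virologic response does not use this algorithm.

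The effect is confined to the secondary snapshot endpoint. With n = 64, each affected subject moves the ≥ 50 proportion by about 1.6 points, and 1/64 against 0/64 changes the exact upper limit from 8.4% to 5.6%. The number affected cannot be known from the documents and may be zero.

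**What to change.** Replace item 26(b) with:

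> An HIV-1 RNA value drawn on the start date of a new non-study ARV and no later than 1 day after the last dose of study drug is used as an on-treatment value; the subject is then classified only by Section 6.2.2.3, and rules b.1) to b.3) prevail.

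This keeps the probable purpose of 26(b), respects the existing limit of last dose plus 1 day, and leaves the category to 6.2.2.3. Treating every switch-day sample as on-treatment, without the 1-day limit, would break that rule and could turn a lack-of-efficacy stop into a < 50 result.

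The cost is one sentence of SAP text and a check of the snapshot program against it. No new data are needed. The reported ≥ 50 proportion may be slightly higher than if 26(b) had been applied literally.

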## 27) TEAE

### **Events with Missing Onset Day and/or Month**

The event is treatment emergent if the following 3 criteria are met:

- The month and year (or year) of onset date is the same as or after the month and year (or year) of the first dose of study drug, and
- The month and year (or year) of the onset date is the same as or before the month and year (or year) of 30th day after the date of the last dose of study drug, and
- End date is as follows:

The (complete) end date is on or after the first dose date, or

The month and year (or year) of end date is the same or after the month and year (or year) of the first dose of study drug, or

End date is completely missing

### **Events with Completely Missing Onset Date**

An AE with a completely missing onset date is defined as TEAE if end date is as follows:

- The (complete) end date is on or after the first dose date, or
- The month and year (or year) of end date is the same or after the month and year (or year) of the first dose of study drug, or
- End date is completely missing

28) Urine Protein Correction

- a) The calibrator material used in the quantitative assay for the measurement of urine protein (UP) was changed globally in Covance on May 27, 2016. All samples reported prior to May 27, 2016 (ie, *RPTDTM* < ‘May 27, 2016’) were tested by the calibrator material manufactured by Roche Diagnostics, while the samples reported on or after May 27, 2016 were tested by the calibrator material manufactured by Quantimetrix. Covance had 3 regional lab centers to run the samples. Each regional lab center conducted its own alternate (quantitative) method comparison, all of these comparison demonstrate that calibrator materials manufactured by the Roche and Quantimetrix yield comparable results as noted in the table below:

Regional Lab Center	Accession Numbers a	Regular Regression for UP Correction b	Correlation Coef.	Bias
Indianapolis Auto Chemistry	Start with 65	$Y = 1.028 X - 3.70$	0.9982	-2.34 (-4.91%)
Geneva Auto Chemistry	Start with 62 or 63	$Y = 0.981 X - 1.44$	0.9993	-2.42 (-4.74%)
Singapore Auto Chemistry	Start with 64 or 66	$Y = 0.980 X - 1.62$	0.9996	-2.73 (-5.08%)
BML in China	Start with 67 or 68	NA	NA	NA

- a Accession numbers specified which regional lab center tested the sample. For example, samples with accession number started with 65 were tested in Indianapolis Auto Chemistry Center.  
 b X and Y are the UP results using calibrator materials manufactured by Roche Diagnostics and Quantimetrix, respectively.

- b) In order to combine the UP results obtained from the 2 different assay methods for summary/comparison purpose, we will convert the UP results analyzed using the calibrator from Roche (ie, results reported prior to May 27, 2016) to Quantimetrix results by using the regression equation listed in above table.

Original UP based on Reported Date	Original UP Categories	Accession Number	AVALC of Corrected UP ('UP' stands for Original UP)
UP reported on/after May 27, 2016	ALL	ALL	AVALC of UP
UP reported before May 27, 2016	UP < 4.0	ALL	'< 4.0'
	UP ≥ 4.0	Start with 65	$1.028 \times UP - 3.70$ ; if $1.028 \times UP - 3.70 \geq 4.0$ '< 4.0'; if $1.028 \times UP - 3.70 < 4.0$
		Start with 62 or 63	$0.981 \times UP - 1.44$ ; if $0.981 \times UP - 1.44 \geq 4.0$ '< 4.0'; if $0.981 \times UP - 1.44 < 4.0$
		Start with 64 or 66	$0.980 \times UP - 1.62$ ; if $0.980 \times UP - 1.62 \geq 4.0$ '< 4.0'; if $0.980 \times UP - 1.62 < 4.0$

- c) The corrected UP results will be used for the following analysis and referred as “UP” in following text. If AVALC of the corrected UP is “< 4.0”, the AVAL of the corrected UP will be imputed as 3.9 mg/dL.

29) Unit conversion for some renal biomarkers derived from related tests with conventional units

- Urine RPB ( $\mu\text{g/L}$ ) to creatinine (mg/dL) ratio:  $1 (\mu\text{g/L}) / (\text{mg/dL}) \quad 100 \times \mu\text{g/g}$
- Urine Beta-2-microglobulin (mg/L) to creatinine (mg/dL) ratio:  $1 (\text{mg/L}) / (\text{mg/dL}) \quad 10^5 \mu\text{g/g}$
- Urine Protein (mg/dL) to creatinine (mg/dL) ratio:  $1 (\text{mg/dL}) / (\text{mg/dL}) \quad 1000 \times \text{mg/g}$
- Urine Albumin (mg/dL) to creatinine (mg/dL) ratio:  $1 (\text{mg/dL}) / (\text{mg/dL}) \quad 1000 \times \text{mg/g}$

30) Calculation of ratios

To calculate laboratory ratios (eg, urine RPB to creatinine ratio), lab value of each test in the ratio needs to be from the same accession number; if any test value used for the ratio calculation from the same accession number is missing, the ratio is not calculable (ie, missing). For urine creatinine, a value of “< 1” is handled as a missing value in the calculation of related ratios. For urine protein, a value of “< 4.0” is handled as a missing value in the calculation of UPCR.

31) Combined category of UP and UPCR

- a) First merge UP and UPCR based on the subject identifier and accession number.
- b) At each visit, based on UP to select which pair of records should be used for the analysis. That is, once a UP record is selected for that visit, the UPCR with the same accession number (if calculated) will be selected. Please note, UPCR is missing when UP < 4.0 mg/dL.
- c) Subject will be classified as “UPCR  $\leq$  200 mg/g” if UP < 4.0 mg/dL or UPCR  $\leq$  200 mg/g; Subject will be classified as “UPCR > 200 mg/g” if UPCR > 200 mg/g; Otherwise, subject will be classified as “Missing”.

32) Prior ARV

Non-study drug ARVs collected in prior ARV form with start date and stop date completely missing are considered “not concomitant”.

33) Lipid modifying medication analyses:

- Lipid modifying medication is defined to be the concomitant medication with any concomitant medication class “LIPID MODIFYING AGENTS” and CMDECOD contains wording of “STATIN” in the ADCM dataset.

- Subjects who took lipid modifying medications at study entry refer to the subjects who use of the lipid modifying agents at study day 1 (ie, the first dose date). More specifically, subjects with “Lipid Modifying Agent Use at Study Entry” include those subjects in Safety Analysis Set with: 1) any selected CM record with the start date  $\leq$  the first dose date, and 2) the end date of the selected CM record is ongoing or the end date of the selected CM record  $\geq$  the first dose date.
- Subjects who initiated lipid modifying medications during the study include the subjects in the Safety Analysis Set who didn’t take lipid modifying medications at study entry and met the following criteria: 1) for subjects who permanently discontinued study drug with any selected CM record started after the first dose date and on and prior to the last dose date; 2) for subjects who are still on study drug with any selected CM records started after the first dose date.
- For lipid modifying medications with the start date completely unknown, we assume the start date is on or before the first dose date, lipid modifying medication was considered as being taken at study entry if the end date is not prior to the first dose date (ie, the end date is on or after the first dose date, completely unknown, or ongoing).
- Lipid modifying medications with the start date prior to the first dose date and the end date completely unknown were considered as being taken at study entry.

34) Age for laboratory test reference range will be based on the age at the sample collection date.

35) For figures, if at a visit where n (sample size) for any treatment group  $< 5$ , data for that treatment group will not be displayed at the visit in figure, but all data will be included in the corresponding table summary.

36) For the PRO data, data up to 30 day after the last dose date for subjects who permanently discontinued of study drug will be summarized.

37) For PRO data, unless otherwise stated, multiple responses and out of range responses will be set to missing and missing responses will not be imputed.

Out of range value is determined based on the following table for within-range response values:

SF-36v2 Health Survey:

Question	Response	
	Min	Max
1, 2, 4a to 4d, 5a to 5c, 6, 8, 9a to 9i, 10, 11a to 11d	1	5
3a to 3j	1	3
7	1	6

VAS adherence questionnaire:

Questions	Response	
	Min	Max
1	0	100
2	0	30
3	0	4

38) Computing EQ-5D index values with SAS using the UK TTO value set

The variables for the 5 dimensions of the EQ-5D descriptive system should be named 'mobility', 'selfcare', 'activity', 'pain', and 'anxiety'. The variable 'UK\_TTO' contains the values of the EQ-5D index.

You can copy and paste the syntax below directly into the SAS syntax window.

```
*****
* SAS syntax code for the computation of index *
* values with the UK MVH A1 TTO value set *
*****;

data Euroqol.Uk_data;
set Euroqol.EQ5D_states;

UK_TTO = 1;

if (mobility = 2) then UK_TTO = UK_TTO 0.069;
if (mobility = 3) then UK_TTO = UK_TTO 0.314;

if (selfcare = 2) then UK_TTO = UK_TTO 0.104;
if (selfcare = 3) then UK_TTO = UK_TTO 0.214;

if (activity = 2) then UK_TTO = UK_TTO 0.036;
if (activity = 3) then UK_TTO = UK_TTO 0.094;

if (pain = 2) then UK_TTO = UK_TTO 0.123;
if (pain = 3) then UK_TTO = UK_TTO 0.386;

if (anxiety = 2) then UK_TTO = UK_TTO 0.071;
if (anxiety = 3) then UK_TTO = UK_TTO 0.236;

if (mobility ne 1) or (activity ne 1) or (selfcare ne 1) or (pain ne 1) or
(anxiety ne 1) then UK_TTO = UK_TTO 0.081;
if (mobility = 3) or (selfcare = 3) or (activity = 3) or (pain = 3) or
(anxiety = 3) then UK_TTO = UK_TTO 0.269;

if (mobility = .) or (selfcare = .) or (activity = .) or (pain = .) or
(anxiety = .) then UK_TTO = . ;

output;
run;
```

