### 3.6. Data Handling Conventions and Transformations

Laboratory data that are continuous in nature but are less than the lower limit of quantitation or above the upper limit of quantitation will be imputed as follows except for urine creatinine:

- A value that is 1 unit less than the limit of quantitation (LOQ) will be used for calculation of descriptive statistics if the datum is reported in the form of “< x” (x is considered as the limit of quantitation). For example, if the values are reported as < 20 and < 5.0, values of 19 and 4.9 will be used for calculation of summary statistics, respectively. An exception to this rule is: for values reported as < 1 or < 0.1, a value of 0.9 or 0.09, respectively, will be used for calculation of summary statistics.
- A value that is 1 unit above the LOQ will be used for calculation of descriptive statistics if the datum is reported in the form of “> x” (x is considered as the LOQ). Values with decimal points will follow the same logic as above.
- The LOQ will be used for calculation of descriptive statistics if the data is reported in the form of “≤ x” or “≥ x” (x is considered as the LOQ).

For urine creatinine, value of “< 1” is handled as a missing value in its summary and the calculation of related ratios.

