### 7.3.4. Proteinuria by Quantitative Assessment

The baseline, postbaseline, changes from baseline, and percentage change from baseline in urine protein to creatinine ratio (UPCR) and urine albumin to creatinine ratio (UACR) will be summarized overall and by Parts 1 and 2 for each visit using descriptive statistics.

The number and percentage of subjects with UPCR  $\leq$  200 mg/g versus  $>$  200 mg/g will be summarized by baseline category at Weeks 12, 24, and 48, and based on the last on-treatment value (up to 1 day after the last dose date of study drug {[KDIGO Guideline Development Staff 2013](#)}).

The number and percentage of subjects with UACR  $<$  30 mg/g versus  $\geq$  30 mg/g will be summarized by baseline category at Weeks 12, 24, and 48, and the last on-treatment value (after first dose date up to 1 day after the last dose date of study drug {[KDIGO Guideline Development Staff 2013](#)}).

Median (Q1, Q3) percentage change from baseline in UPCR and UACR over time will be plotted.

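### Setting UPCR to missing whenever urine protein is below 4.0 mg/dL overstates the median UPCR levels and makes the number of change-from-baseline pairs depend on the outcome

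*SAP*

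**What the plan says.** Four parts of the SAP bear on a urine protein result below 4.0 mg/dL.

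- **Section 3.6** sets the general rule. Laboratory values outside the quantitation limits "will be imputed as follows except for urine creatinine", using one reporting unit below the limit: "if the values are reported as < 20 and < 5.0, values of 19 and 4.9 will be used". Only urine creatinine is also declared missing for ratios.
- **Appendix 5, item 28(c)** applies that rule to urine protein: "the AVAL of the corrected UP will be imputed as 3.9 mg/dL". It adds that the corrected protein values feed the analyses that follow.
- **Appendix 5, items 30 and 31(b)** depart from it. In item 30 a protein value below 4.0 "is handled as a missing value in the calculation of UPCR"; item 31(b) repeats this: "Please note, UPCR is missing when UP < 4.0 mg/dL".
- **Appendix 5, item 31(c)** brings the same records back for the categorical analysis. A subject is placed in the category of 200 mg/g or less "if UP < 4.0 mg/dL or UPCR" is itself at or below 200.

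Section 7.3.4 uses UPCR in three ways: continuous summaries by visit (level, change, percentage change), a table of 200 mg/g or less versus above 200 by baseline category, and a plot: "Median (Q1, Q3) percentage change from baseline in UPCR and UACR over time will be plotted". It does not mention the exclusion.

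**The concern.** Whether a UPCR exists depends on its own numerator. Subjects drop out of the continuous summaries because they excrete little protein, so this missingness is informative. The SAP treats the same record as informative for the category and as absent for the level, the change and the plot.

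The body of the SAP points the other way. A reader of Section 3.6 would expect 3.9 to be carried into the ratio, since urine creatinine is the only named exception. Urine albumin has no such exception either, so UPCR and UACR, reported together in Section 7.3.4, would treat below-limit numerators differently.

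At stake is a descriptive renal safety output. Median UPCR would look higher than it is, and n would shift between visits for reasons linked to the outcome, without the reader being told.

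**Working it through.** **The plan's own figure.** One reporting unit below 4.0 is 4.0 − 0.1 = 3.9 mg/dL, which matches item 28(c).

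**What the ratio would be.** Item 29 gives UPCR (mg/g) = 1000 × protein / creatinine, both in mg/dL. With protein 3.9, UPCR is 390 at creatinine 10, 200 at 19.5, 78 at 50, 39 at 100 and 19.5 at 200. A retained sample with protein 4.0 and creatinine 300 has UPCR 13.3. The rule thus drops the lowest proteins, but not always the lowest ratios.

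**Measured values can be dropped too.** Item 28(b) recodes results reported before 27 May 2016 that fall below 4.0 after correction. Solving a × UP − b = 4.0 gives (4.0 + 3.70)/1.028 = 7.49 mg/dL for accession 65, (4.0 + 1.44)/0.981 = 5.55 for 62/63, and (4.0 + 1.62)/0.980 = 5.73 for 64/66. Quantified results below these cut-offs would also lose their ratio. The documents do not say whether the trial has such samples.

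**Effect on the level (distributions assumed).** Protein is log-normal, median 6 or 8 mg/dL, log SD 0.6 or 0.8. Creatinine is log-normal and independent, median 120 mg/dL, log SD 0.45. The share below 4.0 is Φ[ln(4/median)/SD]; for example Φ(−0.405/0.6) = 25%. The true median UPCR is 1000 × 6/120 = 50 or 1000 × 8/120 = 67. Observed medians come from 400,000 simulated subjects per row.

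| Protein median, log SD | Share < 4.0 | True median UPCR | Records dropped | 3.9 used |
|---|---|---|---|---|
| 6, 0.6 | 25% | 50 | 63 | 52 |
| 6, 0.8 | 31% | 50 | 71 | 53 |
| 8, 0.6 | 12% | 67 | 75 | 67 |
| 8, 0.8 | 19% | 67 | 83 | 68 |

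Allowing a modest positive correlation between protein and creatinine, the ranges become about 59–71 against 52–55 for a true 50, and 73–83 against 67–69 for a true 67.

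A second set of assumptions is less kind to 3.9: creatinine median 110 with log SD 0.7, UPCR median 50 or 80, log SD 0.5 between and 0.5 within subjects, and correlation of UPCR with creatinine from 0 to −0.9. With true changes of −25%, 0 or +25%, it drops 5% to 49% of records per visit. At zero correlation and no change, a true 50 reads 67 dropped and 63 with 3.9, and a true 80 reads 95 and 88. At −0.9, a true 80 reads 84 and 82. In every scenario dropping overstates the level, and 3.9 overstates it less.

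**Effect on the number of pairs.** A pair is lost if either visit is below 4.0. The inputs are the first set, with within-subject log SD 0.5 for protein and the same distribution at both visits. The between-visit correlation of log protein is 1 − 0.5²/SD², which is 0.31 or 0.61. The loss, 1 − P(both ≥ 4.0) from the bivariate normal, is 22% to 43% with no change and 35% to 56% after a true 30% fall. For 64 subjects (SAP Section 1.3) that is about 14 to 28 and 22 to 36 pairs. Splitting the variation differently gives 19% to 40% and 32% to 51%.

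**Effect on median percentage change.** The first set is used, with within-subject log SD 0.35 for creatinine.

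- No true change: both methods are within about 0.3 points of zero.
- True −30%: dropping gives −18% to −24%, and 3.9 gives −18% to −25%.
- Second set, true −25% and +25%: dropping gives −21% to −28% and +21% to +28%. At zero correlation and a true median of 50, a true −25% reads −21% dropped and −16% with 3.9.

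**The case against.** The strongest defence is that the rule is explicit, stated twice and paired with a repair. A specific instruction in item 30 qualifies the general one in Section 3.6. It is reasonable not to form a ratio from a censored numerator, because the imputed ratio is then little more than the reciprocal of urine creatinine. Item 31(c) keeps these subjects in the categorical table, and nothing here is tested. All of this stands. It limits the point to the continuous summaries and the plot, and it shows that 3.9 is not a clean remedy. It does not remove the overstated level or the undisclosed, outcome-dependent n.

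Three stronger readings are tempting but unsupported.

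- A reader might infer that the whole renal safety summary is biased upward. The categories are protected by item 31(c), and serum creatinine, eGFR, dipstick proteinuria and UACR do not use this rule.
- A reader might infer that subjects who improve leave the analysis, so that a false rise appears. Subjects who start below 4.0 and worsen leave as well. A simulation can show a false median change of +7% to +12%, but only by adding within-subject noise to the post-baseline visit alone, so that variance grows after baseline. With one distribution at both visits the effect is about zero.
- A reader might infer that the lowest UPCR values are always the ones lost. In dilute urine they need not be.

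**Conclusion.** The point holds for the continuous UPCR summaries and plot in Section 7.3.4. Items 30 and 31(b) conflict with the expectation set by Section 3.6 and item 28(c), and they remove left-censored records. Median UPCR levels are overstated under every set of assumptions tried, and the number of change-from-baseline pairs depends on the outcome. For change and percentage change no direction of bias can be claimed: both methods usually pull a real change toward zero, dropping can also exaggerate it, and neither is consistently closer.

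The size cannot be determined from the documents, which give no distribution of urine protein or creatinine. The figures above rest on assumed log-normal values and should be read as illustrations. The primary endpoint is untouched, and the matter is minor.

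**What to change.** 1. Compute UPCR levels for the continuous summaries from the 3.9 mg/dL value already derived in item 28(c).
2. Report the number of subjects with protein below 4.0 mg/dL next to n at each visit.
3. Show change and percentage change, including the plot, both with 3.9 and with those records excluded.
4. State the handling of protein below 4.0 in Sections 3.6 and 7.3.4, and align items 30 and 31(b) with it.
5. Keep item 31(c) for the 200 mg/g categories. Reclassifying from 3.9 would push samples with creatinine below 19.5 mg/dL above 200 on the imputed value alone.

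The cost is a small programming change, one extra row per visit and a second version of the change output. The downside should be stated with the results: imputed ratios largely reflect urine creatinine, 3.9 is an upper bound that leaves some upward bias in levels, and it may attenuate change. The counts below 4.0 and the side-by-side display let the reader judge this.
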